4.1.2 Dose Escalation

Following tumor resection, eligible patients who have signed the Informed Consent Form (ICF) will be assigned a dose of LC.

There will be a maximum of 4 dose levels assessed in this study. The first cohort of patients will start at Dose Level 1 (Table 4). If indicated based on the number of observed DLTs at Dose Level 1, patients may be enrolled in Dose Level -1.

Table 4. Liposomal Curcumin, Radiotherapy, and Temozolomide Dose Escalation Schedule

Dose Level	Dose	
	LC	TMZ
Level -1	240 mg/m ²	75 mg/m ² concurrent RT 150-200 mg/m ² Cycles 1-6 adjuvant
Level 1 (Starting Dose)	300 mg/m ²	
Level 2	350 mg/m ²	
Level 3	400 mg/m ²	

LC = liposomal curcumin; RT = radiotherapy; TMZ = temozolomide

The decision whether a new patient should be assigned to the current dose level or to a higher or lower dose level (escalation or de-escalation) is a function of the number of patients already treated at the current dose level, the number of patients who experienced a DLT at the current dose level, and the number of patients who have neither experienced a DLT nor completed their 10-week DLT evaluation period. The Safety Review Committee (SRC) will oversee dose level decisions throughout the dose escalation phase of the study.

All participating sites are expected to notify the Sponsor when a DLT has occurred.

The study will enroll and treat patients in cohorts of 3 in the dose escalation phase. The first cohort will receive 300 mg/m² (Dose Level 1) of LC weekly. The target DLT risk is 30%. During the assessment window, planned doses will be dropped if the data suggest a $\geq 95\%$ probability that the dose will produce a DLT risk $> 30\%$. Using the proposed time-to-event Bayesian optimal interval (TITE-BOIN) design, enrollment in the escalation phase will stop when 12 patients are assigned to the same dose level or when a total of 24 patients have been treated, whichever happens first.

Once the MTD is determined, an additional 6 patients will be treated in an expansion cohort at this dose level or at a lower dose level determined to be the RP2D. For the expansion cohort, patients will continue to be monitored for occurrence of DLTs. If 2 of the first 5 patients or if ≥ 2 of 6 patients experience a DLT, the Principal Investigator will discuss with all study Investigators and with the Medical Monitor and/or SRC whether further addition of patients is needed to re-assess the MTD. Monitoring of all safety and toxicity data will be done by the Principal Investigator and the SRC on a real-time basis.

In the absence of treatment delays due to AEs, treatment for an individual patient may continue until the completion of standard therapy (until the end of Adjuvant Cycle 6) or until one of the following criteria applies:

- Disease progression

- Intercurrent illness that prevents further administration of treatment
- Unacceptable AEs
- Patient decides to withdraw from the study
- General or specific changes in the patient's condition render the patient unacceptable for further treatment in the judgment of the Investigator
- Clinical progression
- Patient noncompliance
- Pregnancy
- Termination of the study by the Sponsor
- The drug manufacturer can no longer provide the study agent

Toxicities requiring dosing delay or modifications will result in dose adjustments as outlined in [Section 5.10](#) (the minimum dose is 240 mg/m²).

Additional details of the study design and escalation decisions are in [Section 9](#).

4.1.3 Administration of Study Therapies

- Treatments will be weekly 3-hr infusions of LC via gravity infusion (without infusion pump) at the assigned dose through concurrent CRT and the 4-week post-CRT recovery time, at which point the DLT evaluation period is completed.
- Patients will continue weekly LC infusions through the adjuvant TMZ treatment period (150-200 mg/m² on Weeks 1-4 of each 28-day cycle) for a maximum of 24 additional weeks (ie, up to 6 additional 4-week cycles).

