1.2 Schema

Figure 1. Study Design

IV = intravenous; MRI = magnetic resonance imaging; TMZ = temozolomide; XRT = radiation therapy
Treatment starts in first week of chemoradiation.

The DLT evaluation period is 10 weeks. Afterward, patients will continue adjuvant TMZ and LC for an additional 24 weeks.

Procedure	Baseline	CRT Period						Post-CRT				Adjuvant Cycles 1 - 6				End Of Treatment ¹⁴	LTFU	End of Study
		Week						Week				Adjuvant Week						
	≤14 Days of D1	1	2	3	4	5	6	7	8	9	10	1	2	3	4			
		D1	D8 ±3	D15 ±3	D22 ±3	D29 ±3	D36 ±3	D43 ±3	D50 ±3	D57 ±3	D64 ±3	D71 ±3	D78 ±3	D85 ±3	D92 ±3		±14 Days	
Clinical chemistry ³	X			X	X			X				X				X		
Complete urinalysis	X																	
Urine pregnancy test (WOCBP only) ⁶	X	X						X				X						
12-lead ECG ⁷	X				X							X						
Administration of RT ⁸		X	X	X	X	X	X											
Administration of TMZ/ondansetron ⁹		X	X	X	X	X	X					X						
Administration of LC/premedication ¹⁰		X	X	X	X	X	X	X	X	X	X	X	X	X	X			
Concomitant medications	X ¹¹	X	X	X	X	X	X	X	X	X	X	X	X	X	X	X		
Adverse events ¹²		X	X	X	X	X	X	X	X	X	X	X	X	X	X	X		X

Procedure	Baseline	CRT Period						Post-CRT				Adjuvant Cycles 1 - 6				End Of Treatment ¹⁴	LTFU	End of Study
		Week						Week				Adjuvant Week						
	≤14 Days of D1	1	2	3	4	5	6	7	8	9	10	1	2	3	4			
		D1	D8 ±3	D15 ±3	D22 ±3	D29 ±3	D36 ±3	D43 ±3	D50 ±3	D57 ±3	D64 ±3	D71 ±3	D78 ±3	D85 ±3	D92 ±3		±14 Days	
Overall survival and progression-free survival ¹³																	X	

CRT = chemoradiotherapy; ECG = electrocardiography; Hgb = hemoglobin; IV = intravenous; KPS = Karnofsky Performance Scale; LC = liposomal curcumin; LTFU = long-term follow-up; MRI = magnetic resonance imaging; PO = per os (oral); RT = radiotherapy; TMZ = temozolomide; WOCBP = women of childbearing potential

1. MRI: Performed at baseline (-21 days) prior to first study drug administration, before every odd-numbered adjuvant cycle (1, 3, 5, etc; approximately every 8 weeks), and at the discretion of the Investigator. End of Treatment MRI does not need to be repeated if performed within the 14 days prior to the End of Treatment date.
2. Vital signs: Include systolic and diastolic blood pressure, respiratory rate, heart rate, temperature, weight, and height. Height is required only at the baseline visit. Vital signs must be performed within 120 min of LC administration.

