3. Hematology and clinical chemistry performed prior to each adjuvant cycle, and at end of treatment. Can be performed up to 3 days prior to LC administration. End of Treatment assessment does not need to be repeated if performed within 5 days of the last assessment.
4. Assessment of anemia: Peripheral smear and haptoglobin performed at baseline. These tests should be repeated if Hgb decreases 2 g/dL within 1 week or if Hgb < 9 g/dL.
5. Perform assessment prior to every adjuvant cycle. End of Treatment assessment does not need to be repeated if performed within 5 days of the last assessment.
6. Pregnancy test: For WOCBP. Test to be performed within 72 hr prior to first administration of LC, at Week 7, and before every adjuvant cycle.
7. ECG: 12-lead ECG to be performed Week 4 before treatment, then Adjuvant Week 1 before start of each odd-numbered adjuvant cycle (Adjuvant Cycles 1, 3, and 5). Any new clinically relevant finding should be reported as an AE. Males with QTcB interval > 450 msec and females with QTcB

interval > 460 msec should discontinue treatment with LC. Any patient with an increase from baseline in the QTcB interval > 15 msec should discontinue LC.

8. RT: ~2 Gy external beam RT, Monday through Friday.
9. TMZ: Given PO, 30 minutes after administration of antiemetic. No food should be taken for 2 hr before and after dosing. CRT period: 75 mg/m² daily during RT; Adjuvant cycles: 150-200 mg/m² Days 1 through 5 of each cycle. Patients will be prescribed ondansetron at 8 mg to administer 30 minutes prior to chemotherapy ingestion as well as every 8 hr as needed. Patients can additionally be prescribed prochlorperazine at 5-10 mg as needed every 6 hr per Investigator preference.
10. Infusion of LC: Given as 3-hr IV infusion (\pm 1 calendar day) by gravity infusion (without infusion pump). Dose as determined by assigned or infusion-adjusted cohort (240 mg/m², 300 mg/m², 350 mg/m², or 400 mg/m²). Premedications to be given are dexamethasone 4 mg IV and diphenhydramine 25 mg IV.
11. Concomitant medications: Record all medications taken within 14 days prior to baseline visit.
12. Adverse events will be collected from the start of treatment and followed for 30 days after the last dose of LC. Patients removed from the study for unacceptable AEs will be followed until resolution or stabilization of the AE.

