4.1.5 Evaluation of Toxicity and Response

- For dose escalation purposes, the DLT evaluation period is defined as the first 10 weeks of treatment (ie, 6 weeks of CRT plus LC followed by a 4-week post-CRT period).
 - Patients are available for DLT evaluation if they have either:
 - Received at least 80% of the planned doses of LC (8 of the planned 10 doses), at least 80% of the planned RT, and at least 60% of the planned TMZ
- OR

- Experienced a DLT in the first 10 weeks of treatment
- Dose finding will be performed using a TITE-BOIN schema as outlined in [Section 8.4.9](#). The window for DLT evaluation and decisions regarding dose advancement or de-escalation will be based on events occurring during the first 10 weeks of the study, though further data regarding safety and tolerability will be collected on every patient continuing infusions through the adjuvant TMZ treatment period.
- Standard contrast magnetic resonance imaging (MRI) will be used for assessment of progression, following the Response Assessment in Neuro-Oncology (RANO) criteria for PD. Patients will have a baseline MRI study followed by CRT, an MRI at the beginning of the adjuvant TMZ phase (4 weeks after completion of CRT) and another MRI every 2 cycles thereafter as per standard of care. More frequent imaging may be clinically necessary per the discretion of the treating physicians.
- MRI scans will be assessed locally by board-certified neuroradiologists who will independently assess tumor size and radiographic changes.
- For the first 2 years after the last dose of LC, patients will be followed for survival and progression every 2 months by telephone call, clinic visit, or medical records. After 2 years have elapsed, patients will be followed every 6 months for survival and progression by telephone call, clinic visit, or medical records.
- For the purposes of analyses, the duration of each arm will last through the 6 weeks of CRT, the 4-week post-CRT period, and the adjuvant cycles received by the patient.

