5.5 Study Interventions Administered

Table 5. Regimen Description - Concurrent CRT Period

Agent	Premedications / Precautions	Dose	Route	Schedule	Cycle Length
LC	Dexamethasone 4 mg IV Diphenhydramine 25 mg IV	Per treatment assignment	IV over 3 hr	Weekly: Weeks 1, 2, 3, 4, 5, 6	6 weeks
TMZ	No food 2 hr before and after dosing Antiemetic (eg, ondansetron, prochlorperazine) 30 minutes before dosing Stool softener PRN	75 mg/m ²	PO	Daily during term of RT	
RT		2 Gy	External beam therapy	Monday-Friday	

IV = intravenous; LC = liposomal curcumin; PO = per os (oral); PRN = pro re nata (as needed); RT = radiotherapy; TMZ = temozolomide

Table 6. Regimen Description - Post-CRT Period

Agent	Premedications / Precautions	Dose	Route	Schedule	Cycle Length
LC	Dexamethasone 4 mg IV Diphenhydramine 25 mg IV	Per treatment assignment	IV over 3 hr	Weekly: Weeks 7, 8, 9, 10	4 weeks

IV = intravenous; LC = liposomal curcumin

Table 7. Regimen Description - Adjuvant Period

Agent	Premedications / Precautions	Dose	Route	Schedule	Cycle Length
LC	Dexamethasone 4 mg IV Diphenhydramine 25 mg IV	Per treatment assignment	IV over 3 hr	Weekly: Adjuvant Cycles 1-6: Weeks 1, 2, 3, 4 of each cycle	4 weeks
TMZ	No food 2 hr before and after dosing	150-200 mg/m ² (Cycles 1-6)	PO	Daily	

Agent	Premedications / Precautions	Dose	Route	Schedule	Cycle Length
	Antiemetic (eg, ondansetron, prochlorperazine) 30 minutes before dosing Stool softener prn				

CRT = chemoradiotherapy; IV = intravenous; LC = liposomal curcumin; PO = per os (oral); PRN = pro re nata (as needed); TMZ = temozolomide

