For patients receiving concurrent TMZ and LC, blood counts will be evaluated weekly. Within -5 days (5 days prior to) the first dose of each 5-day TMZ treatment, the patient must have an ANC $\geq 1500/\mu\text{L}$ and platelet count $\geq 100,000/\mu\text{L}$. On Day 1 of each cycle (within -5 days) all nonhematological Grade 3 or 4 toxicities (except for alopecia, nausea and vomiting, and lymphopenia), that is definitely, probably, or possibly related to TMZ must have resolved (Common Terminology Criteria for Adverse Events [CTCAE] Grade ≤ 1). If toxicity persists, treatment should be delayed by 1 week for up to 3 consecutive weeks. If after 3 weeks of delay all toxicity has still not resolved, any further adjuvant treatment with TMZ should be stopped.

5.5.4 *Radiotherapy*

No specific prophylaxis is indicated for the RT regimen. The Investigator may use low-dose benzodiazepines if clinically indicated for anxiolytic management if compliance is an issue.

Modalities: Only conformal techniques (3-dimensional conformal radiotherapy [3D CRT] or intensity-modulated radiotherapy [IMRT]) will be allowed in this study. Proton radiotherapy is not allowed. Two-dimensional techniques not employing volumetric target volume definition or 3-dimensional assessments of radiation dose are not allowed. The radiation technology utilized as well as the dosing and target volumes are determined according to current standard of care and described below. In most circumstances IMRT will be optimal as most target volumes are convex or concave, such that there would likely be an advantage in protection of critical structures and brain.

Equipment: All patients must be treated with a linear accelerator with nominal photon energy between 6 to 18 MV. Co-60 is not allowed on this study. Electrons and protons may not be used.

Additional information on treatment planning may be found in [Section 9.2](#) (Appendix 2).

5.5.4.1 *Potential Toxicity of Radiotherapy*

Side effects of radiation may occur in an increased frequency and severity when receiving LC along with standard RT and TMZ.

The following side effects may be associated with RT for brain cancer:

Likely:

- Tiredness including mental slowing
- Lack of energy
- Redness or soreness of scalp
- Hair loss (temporary or permanent)
- Short-term hearing loss
- Possible increase in brain tumor symptoms such as headaches, seizures, or weakness during treatment
- Edema or swelling of the brain that may require steroid medication

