7 STUDY ASSESSMENTS AND PROCEDURES

- Study procedures and their timing are summarized in the SoA. Protocol waivers or exemptions are not allowed.
- Immediate safety concerns should be discussed with the Sponsor immediately upon occurrence or awareness to determine if the patient should continue or discontinue study intervention.
- Adherence to the study design requirements, including those specified in the SoA, is essential and required for study conduct.
- All screening evaluations must be completed and reviewed to confirm that potential patients meet all eligibility criteria. The Investigator will maintain a screening log to record details of all patients screened and to confirm eligibility or record reasons for screening failure, as applicable. A patient who is rescreened is required to sign another ICF.
- Procedures conducted as part of the patient's routine clinical management (eg, blood count) and obtained before signing of the ICF may be utilized for screening or baseline purposes provided the procedures met the protocol-specified criteria and were performed within the timeframe defined in the SoA.

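### Section 4.1.3 and Table 7 put no five-day limit on adjuvant temozolomide and conflict with the Days 1-5 course given elsewhere in the protocol

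*Protocol*

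**What the plan says.** Two places state the adjuvant TMZ dose with a schedule that is not limited to five days:

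- **Section 4.1.3 (Administration of Study Therapies)** has weekly LC continuing through the "adjuvant TMZ treatment period (150-200 mg/m² on Weeks 1-4 of each 28-day cycle". The dose in the parenthesis can only be TMZ, because the LC levels in Table 4 run from 240 to 400 mg/m².
- **Section 5.5, Table 7, TMZ row** gives "150-200 mg/m ² (Cycles 1-6") by mouth, with *Daily* as the whole schedule entry.

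Three places give a five-day course:

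- **SoA (Section 1.3), footnote 9:** "Adjuvant cycles: 150-200 mg/m² Days 1 through 5 of each cycle".
- **SoA grid:** the row "Administration of TMZ/ondansetron" has one mark in the adjuvant columns, under Adjuvant Week 1. The LC row is marked in all four adjuvant weeks.
- **Section 5.5.3 (Temozolomide Dosing Precautions):** the neutrophil and platelet criteria are tied to "the first dose of each 5-day TMZ treatment".

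The four-week pattern appears once more, in the LC row of Table 7: "Weekly: Adjuvant Cycles 1-6: Weeks 1, 2, 3, 4 of each cycle".

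**The concern.** The section on administering study therapies and the regimen table are natural places to look up a dose. Neither gives the day limit. Taken at their word, they allow an oral myelosuppressive drug to be given at its adjuvant dose throughout the cycle.

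Two other provisions make a misreading practical. Section 5.5.2.5 has the pharmacist hand over the TMZ for a complete cycle at once, so a wrong quantity could leave the pharmacy in one step. Section 5.5.2.6 lists leucopenia, thrombocytopenia, anemia and hepatic injury, including fatal hepatic failure, among the known or observed toxicities.

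There is also a data consequence. Section 5.8 measures TMZ compliance by capsule count against the prescribed regimen, which requires one regimen. If any patient were misdosed, the adjuvant-period exposure and adverse event summaries would mix toxicity from excess TMZ with that of the intended combination.

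**Working it through.** **Step 1. Do the statements conflict?** Section 4.1.3 spreads the TMZ dose over Weeks 1-4, while the SoA grid and footnote 9 confine it to the first five days of Week 1. Both cannot be right. *Daily* in Table 7 could be reconciled with five days, but the row omits the limit. This is not a general habit of the regimen tables, since the TMZ row of Table 5 is bounded by the term of radiotherapy. The Table 7 row is split across a page in the text available, so less weight is put on it. The conflict between Section 4.1.3 and the SoA stands without it.

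**Step 2. Inputs.**
- Daily dose 150-200 mg/m² (Section 4.1.3, Table 7, SoA footnote 9).
- Cycle of 28 days, up to 6 cycles (Section 4.1.3).
- Dosing days per cycle: 5 (SoA footnote 9, Section 5.5.3). Under the other wording the number depends on frequency, which Section 4.1.3 does not give. *Daily* from Table 7 over four weeks gives 28.

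**Step 3. Cumulative dose.** Dose per cycle = daily dose × dosing days. Six-cycle total = 6 × dose per cycle.

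| Reading | Days per cycle | Per cycle (mg/m²) | Six cycles (mg/m²) | Ratio to 5 days |
|---|---|---|---|---|
| Days 1-5 (SoA, 5.5.3) | 5 | 750-1000 | 4500-6000 | 1.0 |
| Weeks 1-4, once a week (assumed) | 4 | 600-800 | 3600-4800 | 0.8 |
| Weeks 1-4, five days a week (assumed) | 20 | 3000-4000 | 18,000-24,000 | 4.0 |
| Weeks 1-4, daily (4.1.3 with Table 7) | 28 | 4200-5600 | 25,200-33,600 | 28/5 = 5.6 |

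Over six cycles this is 6 × 5 = 30 dosing days against at most 6 × 28 = 168. The two middle rows are assumed frequencies that show the range Section 4.1.3 leaves open on its own.

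**Step 4. Scale.** Assuming daily dosing for the six concurrent weeks (42 doses), the concurrent phase totals 75 × 42 = 3150 mg/m². One 28-day adjuvant cycle would be 4200/3150 = 1.33 to 5600/3150 = 1.78 times that total. A five-day cycle is 750/3150 = 0.24 to 1000/3150 = 0.32 times.

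**Step 5. Reach into the design.** Section 4.1.5 states that "the DLT evaluation period is defined as the first 10 weeks of treatment", made up of six weeks of chemoradiation and four weeks without TMZ. Adjuvant TMZ starts after that window. DLT counts, TITE-BOIN decisions, MTD selection and the 80/80/60% feasibility endpoint therefore do not depend on which schedule is followed.

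**The case against.** The strongest reply is that the protocol resolves the matter itself. Three places agree on a five-day course. Section 7 adds: "Adherence to the study design requirements, including those specified in the SoA, is essential and required for study conduct". Section 5.8 checks compliance after the weeks in which TMZ is given, which fits dosing in only some weeks, and Section 5.5.1.3 describes TMZ as routine standard of care. The sentence in Section 4.1.3 is about LC, mentions TMZ only in a parenthesis, and gives no daily frequency. The 5.6-fold figure therefore needs *Daily* brought in from Table 7. The six-cycle totals also assume that the error survives the blood-count criteria before every course.

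Much of this is right. Days 1-5 is the evident intent, 5.6 is an upper bound from reading two places together, and persistence through six cycles is unlikely. It does not remove the problem. The Section 7 sentence sits under assessments and procedures and sets no order of precedence for conflicting dose statements. The blood-count criteria apply before a course starts, so they do not by themselves stop the first over-long cycle. A protocol should not rely on its readers to overrule its own administration section.

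**Conclusion.** The concern holds. Section 4.1.3 is wrong as written, and the Table 7 TMZ row lacks the limit that would correct it. The conflict is between a five-day course and an open schedule of up to 28 days per cycle, at most 5.6 times the intended cumulative dose. That maximum rests on combining *Daily* in Table 7 with the four weeks in Section 4.1.3. That Days 1-5 is intended, and that the four-week phrase came from the LC row, are inferences from the document for the sponsor to confirm.

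The consequence is patient safety in the adjuvant period and, if any patient were misdosed, the safety and exposure summaries for that period. It does not extend to dose finding or feasibility. A contradictory dose instruction for a cytotoxic drug must be corrected even though the statistical design is untouched.

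**What to change.** In Section 4.1.3 and in the TMZ row of Table 7, give adjuvant TMZ as 150-200 mg/m² by mouth once daily on Days 1-5 of each 28-day cycle, after the sponsor has confirmed that this is the intended course. Both will then match SoA footnote 9, the SoA grid and Section 5.5.3. In Section 4.1.3, attach Weeks 1-4 to the LC infusions only.

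With the correction, every place implies 5 dosing days and 750-1000 mg/m² per cycle, or 4500-6000 mg/m² over six cycles. The cost is a wording amendment in two places. Design, sample size and analysis do not change.

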4.1.4 Clinical Sites

Treatment will be administered in outpatient infusion centers of the Sidney Kimmel Comprehensive Cancer Center at Johns Hopkins (Baltimore) or Sibley Memorial Hospital (Washington DC).

4.1.5 Evaluation of Toxicity and Response

- For dose escalation purposes, the DLT evaluation period is defined as the first 10 weeks of treatment (ie, 6 weeks of CRT plus LC followed by a 4-week post-CRT period).
 - Patients are available for DLT evaluation if they have either:
 - Received at least 80% of the planned doses of LC (8 of the planned 10 doses), at least 80% of the planned RT, and at least 60% of the planned TMZ
- OR

- Experienced a DLT in the first 10 weeks of treatment
- Dose finding will be performed using a TITE-BOIN schema as outlined in [Section 8.4.9](#). The window for DLT evaluation and decisions regarding dose advancement or de-escalation will be based on events occurring during the first 10 weeks of the study, though further data regarding safety and tolerability will be collected on every patient continuing infusions through the adjuvant TMZ treatment period.
- Standard contrast magnetic resonance imaging (MRI) will be used for assessment of progression, following the Response Assessment in Neuro-Oncology (RANO) criteria for PD. Patients will have a baseline MRI study followed by CRT, an MRI at the beginning of the adjuvant TMZ phase (4 weeks after completion of CRT) and another MRI every 2 cycles thereafter as per standard of care. More frequent imaging may be clinically necessary per the discretion of the treating physicians.
- MRI scans will be assessed locally by board-certified neuroradiologists who will independently assess tumor size and radiographic changes.
- For the first 2 years after the last dose of LC, patients will be followed for survival and progression every 2 months by telephone call, clinic visit, or medical records. After 2 years have elapsed, patients will be followed every 6 months for survival and progression by telephone call, clinic visit, or medical records.
- For the purposes of analyses, the duration of each arm will last through the 6 weeks of CRT, the 4-week post-CRT period, and the adjuvant cycles received by the patient.

